Collection of saliva will include two family members: the primary caregiver and the permanent sibling that is closest in age to the foster child. If two permanent children are the same age difference away from the foster child, the permanent sibling with who the foster child interacts with most will be selected. Consent and assent forms will be signed by parent and child. Saliva will be gathered for three consecutive days before the intervention (days 1, 2, and 3) and after the intervention (days 31, 32, and 33); each sampling day, participants will provide a waking, 30 min after waking, and bedtime sample. A two-week window for saliva collection will be allowed depending on when the participating family completes the intervention. Participants passively drool through a straw into a 2mL polypropylene tube and labeled each tube with the time and date. Participants will be instructed not to eat, drink, or brush their teeth 30 minutes before each sample, and to keep completed samples in the refrigerator throughout the study period. Participants will ship saliva samples to the lab and samples will be then stored at -20°C. Saliva samples will be batch assayed in duplicate according to manufacturer instructions for cortisol concentrations using an enzyme immunoassay (EIA) kit (Salimetrics, State College, PA). Inter- and intra-assay coefficients of variability in previous studies by the Pace research team

were 8.16% and 7.74%, respectively. In line with prior work (Zeiders et al., 2014), the following cortisol parameters will be assessed: waking level (Sample 1), bedtime level (Sample 3), the CAR (the difference between Sample 2 – Sample 1), the diurnal slope (the difference between Sample 3 - Sample 1), and the area under the curve (AUC) to assess total cortisol output across the day. AUC will be calculated using the trapezoidal method.

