A BEHAVIORAL INTERVENTION WITH FOSTER FAMILIES

NCT Number: In progress of registering

Date of Original Document: October 25, 2021

STATISTICAL ANALYSIS PLAN

Plan for Data Management/Analysis

Randomization: The central hypothesis will be tested using a randomized controlled trial (RCT) design. The intent of the RCT design is to measure the effectiveness of the intervention and decrease bias through randomization (Montori & Guyatt, 2001). Because severity of disability may affect stress levels in the home, partial stratified randomization for disability severity will be employed. Stratified randomization creates balance between the control and intervention groups. Furthermore, stratification between each group allows for disaggregation of data (Friedman et al., 2015). If the highest-needs children are overrepresented in either the control or intervention groups, inferences could be incorrectly skewed. Families will complete an adapted Autism Behavior Checklist (ABC) before randomization, designed to screen for developmental and behavioral problems in children. The ABC was developed to provide a valid behavior checklist to measure level of behavioral concerns in children with disabilities (Krug, 1980) and has demonstrated intra-rater reliability of $r = 0.87$. Families will be stratified to ensure equal disability severity among groups. The two study groups will include 1) the control group with no intervention and 2) families receiving the intervention. Families will fill out the prescreening tool, be randomly assigned to a group, and receive the survey tools. The same surveys will be collected after the intervention for comparison among groups. Families not assigned to the intervention will be offered the option to receive the intervention after the initial study has concluded. Families participating in the salivary cortisol collection will be randomly chosen from the intervention group.

Statistical analysis will be blinded through use of an independent statistician. STATA statistical software will be used to calculate descriptive statistics, t-tests, correlations, and

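### Home refrigeration of saliva tubes, read plainly, stores pre-intervention tubes about 30 days longer than post-intervention tubes, so any cortisol loss in storage would be confounded with the pre-post change

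*Protocol*

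**What the plan says.** The handling rules are in the protocol's Salivary Cortisol section. The primary caregiver and one permanent sibling each give three samples a day on days 1, 2 and 3 before the intervention and on days 31, 32 and 33 after it. Timing is flexible: "A two-week window for saliva collection will be allowed depending on when the participating family completes the intervention". Participants are told "to keep completed samples in the refrigerator throughout the study period". The next sentence reads "Participants will ship saliva samples to the lab and samples will be then stored at -20°C". The tubes are then assayed as a batch, in duplicate. Each tube carries its collection time and date.

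The section does not define the study period. It does not say how many shipments there are or when they go, sets no maximum refrigerator time, gives no stability data, and does not ask for shipping, receipt or freezing dates.

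Four other places bear on the point:

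- **SAP, Plan for Data Management/Analysis:** "Families participating in the salivary cortisol collection will be randomly chosen from the intervention group". The SAP also names cortisol as a secondary outcome.
- **Protocol, Purpose and Aims:** aim 3 covers preliminary efficacy on diurnal cortisol as well as feasibility.
- **Protocol, Study Timeline:** the intervention takes 2 months, which does not fit post-intervention sampling that starts on day 31.
- **Protocol, Sources of Materials:** surveys and saliva are collected at T1 and T2, with a further collection (T3) one month after the intervention. The Salivary Cortisol section has no third saliva wave.

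**The concern.** A family that follows the instruction literally keeps its first tubes refrigerated until the last ones are filled and then posts them all. Refrigerator time is then long for every pre tube and short for every post tube, in every participant. Storage time and the pre-post contrast become the same variable.

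A control arm with the same sampling days would share the gap and allow it to be subtracted out. The SAP provides none. Batch or duplicate assay does not help, because the difference arises before freezing. A larger sample does not help either, because the error would be systematic.

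If cortisol is lost in proportion to its level, all five planned parameters are affected. Waking level, bedtime level and AUC are lowered in the pre tubes. The awakening response and the diurnal slope, both differences between samples from the same day, shrink by the same factor. The protocol associates high bedtime levels and high overall output with stress, so loss in the pre tubes would conceal an improvement or look like a deterioration.

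**Working it through.** The documents state no storage time or loss rate, so there is no figure of theirs to reproduce. The gap comes from the sampling days; the consequences are a sensitivity analysis.

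**1. Storage gap.** Inputs: pre days 1, 2, 3 and post days 31, 32, 33 (Salivary Cortisol).

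- Paired gap: 31 − 1 = 32 − 2 = 33 − 3 = 30 days.
- With one shipment on day 33, pre tubes have 33 − 3 = 30 to 33 − 1 = 32 days in the refrigerator, and post tubes 0 to 2.
- Two-week window running late: 30 + 14 = 44 days. Running early: 30 − 14 = 16 days. The text does not say which way it runs.
- Two-month intervention (Study Timeline): about 60 days.

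**2. Spurious change with no true effect.** Let L be the fraction of cortisol lost from a pre tube over its extra refrigerator time (assumed). The apparent post/pre change is 1/(1 − L) − 1.

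| Assumed L | Apparent rise |
|---|---|
| 0% | 0% |
| 2% | 1/0.98 − 1 = 2.0% |
| 5% | 1/0.95 − 1 = 5.3% |
| 10% | 1/0.90 − 1 = 11.1% |
| 15% | 1/0.85 − 1 = 17.6% |

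If loss instead runs at a constant 5% per 30 days (assumed), the rise over a gap of g days is 1/0.95^(g/30) − 1: 2.8% at 16 days, 5.3% at 30, 7.8% at 44 and 10.8% at 60.

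**3. Masking of a true fall.** With a true fall of 10% (assumed), a 10% loss gives 0.90/0.90 = 1, so the fall disappears. A 5% loss gives 0.90/0.95 = 0.947, an apparent fall of 5.3%.

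**4. False-positive rate, as illustration only.** Assumptions: paired t-test on log cortisol level, two-sided 0.05, 40 pairs, SD of the log change 0.4. Noncentrality = −ln(1 − L)/0.4 × √40, with 39 degrees of freedom.

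| Assumed L | Noncentrality | Chance of a significant change |
|---|---|---|
| 0% | 0 | 5% |
| 2% | 0.32 | 6% |
| 5% | 0.81 | 12% |
| 10% | 1.67 | 37% |
| 15% | 2.57 | 71% |

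Over losses of 2 to 15%, the range is 7 to 92% at SD 0.3 and 6 to 52% at SD 0.5. The count matters too: Sample Size Justification gives 40 without saying persons or families, and two members per family are sampled. If 40 means families, there are up to 80 pairs, and the 37% at a 10% loss becomes 64% (SD 0.4).

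**The case against.** A reader might infer that the plan builds in a demonstrated storage bias. The documents do not support that. They contain no evidence that refrigerated cortisol degrades, or by how much. At zero loss there is no bias, and at an assumed 1% loss the illustrative error rate is still only 5.2 to 5.5% (40 pairs, SD 0.5 to 0.3). The large percentages come from assumed losses of 10 to 15%. Only the conditional statement stands: any loss would be confounded.

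A reader might also infer that all tubes are certainly posted once, at the end. That is the plain reading, but shipment after each wave is neither stated nor excluded. The protocol also says it uses the methods of a cited cortisol study, which may settle handling but is not reproduced. This limits how firmly the 30 days can be asserted. It does not remove the problem: as written, families may handle tubes differently, and no shipping or freezing date would reveal it.

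The error rates rest on a test that neither document specifies. They also do not carry over to the awakening response and the slope, which are raw differences, can be negative and cannot be logged. That objection is right, and it is why those rates are illustration only.

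Finally, cortisol is exploratory, and without control saliva a pre-post change could not be credited to the intervention even with identical storage. That lowers the stakes. But the plan intends to read preliminary efficacy from these tubes, and a known, avoidable confound need not be added to an uncontrolled comparison.

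**Conclusion.** The point holds in conditional form. On the plain reading, pre tubes are refrigerated about 30 days longer than post tubes, with a range of roughly 16 to 44 days from the window and about 60 days under the two-month timeline. Because saliva comes only from intervention families, any loss over that time would be fully confounded with the pre-post change, in the direction that hides a fall or mimics a rise. The size is unknown: 0 to 17.6% for assumed losses of 0 to 15%.

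The conclusion rests on the literal reading of the refrigerator instruction and, for its size, on a loss rate the documents do not give. Apart from the handling, three statements conflict and must be reconciled: post-intervention sampling from day 31, the two-month intervention, and the T3 collection that is absent from the Salivary Cortisol section. This is a cheap improvement to an exploratory outcome and has no bearing on the questionnaire outcomes.

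**What to change.** In the protocol's Salivary Cortisol section, change the refrigerator instruction so that tubes are kept refrigerated only until shipment to the lab straight after each three-day collection block. Record shipping, receipt and freezing dates for each tube; the collection date is already on the label. State that each person's pre and post tubes are assayed in the same batch. Reconcile the sampling days, window, intervention length and T3 collection, and say whether 40 means persons or families.

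With equal handling of each block, the difference in refrigerator time falls from about 30 days to about 0, and the confounding it could cause goes with it, whatever the loss rate.

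The cost is a separate mailing for each wave: one extra per saliva family with two waves, two extra if saliva is also taken at T3. No visits or assays are added. Pre tubes would still spend longer at -20°C before a common assay, and transit could differ between mailings. The change does not remove these differences, but the logged dates would document them. It has to be made before collection starts, since cortisol lost in storage cannot be recovered.

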A BEHAVIORAL INTERVENTION WITH FOSTER FAMILIES

NCT Number: In progress of registering

Date of Original Document: October 25, 2021

STATISTICAL ANALYSIS PLAN

Plan for Data Management/Analysis

Randomization: The central hypothesis will be tested using a randomized controlled trial (RCT) design. The intent of the RCT design is to measure the effectiveness of the intervention and decrease bias through randomization (Montori & Guyatt, 2001). Because severity of disability may affect stress levels in the home, partial stratified randomization for disability severity will be employed. Stratified randomization creates balance between the control and intervention groups. Furthermore, stratification between each group allows for disaggregation of data (Friedman et al., 2015). If the highest-needs children are overrepresented in either the control or intervention groups, inferences could be incorrectly skewed. Families will complete an adapted Autism Behavior Checklist (ABC) before randomization, designed to screen for developmental and behavioral problems in children. The ABC was developed to provide a valid behavior checklist to measure level of behavioral concerns in children with disabilities (Krug, 1980) and has demonstrated intra-rater reliability of $r = 0.87$. Families will be stratified to ensure equal disability severity among groups. The two study groups will include 1) the control group with no intervention and 2) families receiving the intervention. Families will fill out the prescreening tool, be randomly assigned to a group, and receive the survey tools. The same surveys will be collected after the intervention for comparison among groups. Families not assigned to the intervention will be offered the option to receive the intervention after the initial study has concluded. Families participating in the salivary cortisol collection will be randomly chosen from the intervention group.

Statistical analysis will be blinded through use of an independent statistician. STATA statistical software will be used to calculate descriptive statistics, t-tests, correlations, and

regressions to examine prediction and address the study aims. Consistent with the aims of the study, the primary outcome is to determine the feasibility and effect of the intervention on family hardiness and relationship development, with a secondary outcome of stress levels measured via cortisol levels. We hypothesize that the intervention will improve family hardiness measures and sibling relationships, and that salivary cortisol collection of families participating in the collection of saliva will be feasible within this population. The primary investigator examine potential mediation analysis and multi-level modeling to identify relationships of the concepts and individual characteristics nested within families.

References

Friedman, L. M., Furberg, C. D., DeMets, D. L., Reboussin, D. M., & Granger, C. B. (2015).

Fundamentals of clinical trials (5th ed. 2015 ed.). Cham: Springer International Publishing. <https://doi.org/10.1007/978-3-319-18539-2>

Krug, D. A. (1980). Behavior checklist for identifying severely handicapped individuals with high levels of autistic behavior. *Journal of child psychology and psychiatry*, 21(3), 221-229. <https://doi.org/10.1111/j.1469-7610.1980.tb01797.x>

Montori, V. M., & Guyatt, G. H. (2001). Intention-to-treat principle. *Canadian Medical Association Journal (CMAJ)*, 165(10), 1339-1341.

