A BEHAVIORAL INTERVENTION WITH FOSTER FAMILIES

NCT Number: In progress of registering

Date of Original Document: January 1, 2022

STUDY PROTOCOL

Purpose and Aims

The purpose of this study is to test the effects of an easily accessible intervention that is unique for including both caregivers and children living in the home. Three aims will be conducted to: (1) establish the feasibility of the technology-based, family-centered intervention; (2) explore in a preliminary manner the effects of the intervention on stress and relational quality outcomes among family member participants; and (3) explore feasibility and preliminary efficacy of the intervention on diurnal salivary cortisol levels within the foster family population.

Design

This study will use a randomized controlled trial design. Randomization will be used to assign participants into the experimental or control group. Blinding of the two groups to participants will not be done. However, the team will blind the statistical analysis to group with the use of a statistician. Families assigned to the control will have the opportunity to participate in the intervention post- data collection and analysis and outside of the research protocol. The intervention was created in partnership and adapted from the Connected Family Series (CFS) by psychologists at the Karyn Purvis Institute of Childhood Development (KPICD). Adaptation is needed as the original intervention was geared toward adoptive families and excluded foster families. This process is currently occurring, but has not been completed. The intervention also needed content specific to fostering children with special needs. Stress and relational quality outcomes among members will be measured using the concepts of family hardiness, preparedness, and relationship development through a self-report questionnaire which include the Family Hardiness Index, the Integrating Foster Children subscale from the Casey Foster Applicant Inventory, and the Sibling Inventory of Behavior respectively.

Study Timeline

The study will span 6 months to 1 year; 1 month for recruitment and collection of baseline data, 2 months for the intervention, 3 months for post intervention data collection and 3 months for data analysis in 2022. Data will be gathered during the spring and summer of 2022 with the weight-listed control group able to participate in the intervention after data collection of the initial trial period. Dissemination of results is expected by 2023.

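### The SAP assigns unblinded families to a group before they receive the baseline surveys, and nothing requires the baseline to be completed before the group is disclosed

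*SAP*

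**What the plan says.** The SAP, under Plan for Data Management/Analysis (Randomization), describes the flow as "Families will fill out the prescreening tool, be randomly assigned to a group, and receive the survey tools". The next sentence reads "The same surveys will be collected after the intervention for comparison among groups", which identifies the surveys in the first sentence as the baseline battery. The only instrument explicitly placed ahead of assignment is the stratification tool: "Families will complete an adapted Autism Behavior Checklist (ABC) before randomization".

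On blinding, the Protocol (Design) states "Blinding of the two groups to participants will not be done" and adds that "the team will blind the statistical analysis to group with the use of a statistician". The second provision covers the analyst, not the family filling in the questionnaire.

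For the saliva subsample the SAP says "Families participating in the salivary cortisol collection will be randomly chosen from the intervention group". On analysis it says "STATA statistical software will be used to calculate descriptive statistics, t-tests, correlations, and" "regressions to examine prediction and address the study aims", without saying whether T1 scores enter as change scores, as a covariate, or not at all.

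**The concern.** A baseline measure earns its place in a randomized comparison because allocation cannot have influenced it. Here the outcomes are caregiver self-reports on family hardiness, sibling relationships and preparedness. One arm is told it will start a programme, and the other that it will get nothing until the trial is over. If caregivers answer T1 knowing which applies to them, disappointment, optimism or greater candour can shift the scores, and the T1 difference between arms is no longer due to chance alone.

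Two conditions must both hold for this to do harm, and the documents settle neither: families know their group when they answer T1, and the analysis uses T1. If both hold, change-score, baseline-adjusted and T2-only analyses stop estimating the same quantity. The result would then depend on an analysis choice that the SAP leaves open. A baseline taken after disclosure cannot be replaced later.

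**Working it through.** **Step 1: does any section put T1 before disclosure?**

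| Section | What it fixes about timing | Requires T1 before disclosure? |
|---|---|---|
| SAP, Randomization | prescreening, then assignment, then surveys | No; states the reverse order for assignment |
| Protocol, Study Timeline | baseline data share a month with recruitment | No |
| Protocol, Participant Recruitment | screening, consent, assignment; surveys not mentioned | No |
| Protocol, Sources of Materials | T1 precedes the intervention | No; randomization not mentioned |
| Protocol, Pre-Intervention Assessment | battery follows screening | No; allocation not mentioned |

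The SAP sentence reads as a time sequence, because the SAP separately requires its first item (the checklist) to precede its second (assignment). Assignment is not disclosure, however, and no section says when families are told.

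One planned step could reveal the group early. Saliva families come from the intervention group, so they can be selected only after assignment, yet saliva is also due at T1. A family told it has been selected could infer its group. Whether its T1 survey comes first is not stated.

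**Step 2: size.** The documents contain no figure to reproduce on this point, so the following is an illustration under assumptions.

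Inputs: g = 1 for intervention and 0 for control; b = mean T1 shift from knowing the group, in SD units (assumed); k = fraction of that shift still present at T2 (assumed); r = T1–T2 correlation (assumed 0.5, 0.7 and 0.86). The value 0.86 is the Family Hardiness Index test-retest reliability quoted in the Protocol, used as a high case. The true effect is set to 0.

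Model: T2 = r·x + √(1−r²)·e + k·b·g in either order. Under the current order T1 = x + b·g; with T1 before disclosure T1 = x.

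| Analysis | Current order | T1 before disclosure | Difference |
|---|---|---|---|
| Change score | k·b − b = (k−1)b | k·b | −b |
| Baseline-adjusted | k·b − r·b = (k−r)b | k·b | −r·b |
| T2 only | k·b | k·b | 0 |

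The difference column does not depend on k:

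| b | Change | Adjusted, r = 0.5 | r = 0.7 | r = 0.86 |
|---|---|---|---|---|
| 0 | 0 | 0 | 0 | 0 |
| 0.1 | −0.10 | −0.05 | −0.07 | −0.086 |
| 0.2 | −0.20 | −0.10 | −0.14 | −0.172 |

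A simulation with 65 families per arm (130/2) and 20,000 runs gave the same differences at k = 0, 0.5 and 1.

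**Step 3: total bias**, at b = 0.1 and r = 0.7, current order → T1 before disclosure:

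| k | Change | Adjusted | T2 only (either order) |
|---|---|---|---|
| 0 | −0.10 → 0 | −0.07 → 0 | 0 |
| 0.5 | −0.05 → +0.05 | −0.02 → +0.05 | +0.05 |
| 1 | 0 → +0.10 | +0.03 → +0.10 | +0.10 |

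Break-even for absolute total bias: |k−1| = k gives k = 0.5 for change scores; |k−r| = k gives k = r/2 for adjusted analyses, that is 0.25, 0.35 and 0.43 for the three values of r. Above these, re-ordering makes total bias larger, because a contaminated T1 happens to offset a reaction that persists at T2.

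**Step 4: error rate, k = 0 only.** With 65 per arm, a two-sided 5% z-test and SE = SD·√(2/65), the SD is √(2(1−r)) for change and √(1−r²) for adjusted. At b = 0.1 and r = 0.7:

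- Change: SE = 0.775 × 0.175 = 0.136; 0.10/0.136 = 0.74; rejection rate 11.4%.
- Adjusted: SE = 0.714 × 0.175 = 0.125; 0.07/0.125 = 0.56; rejection rate 8.6%.
- T2 only: 5.0%.

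For b > 0 the false rejections lean against the intervention; for b < 0 they lean in its favour.

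**The case against.** The strongest reply is that the Protocol, which is dated after the SAP (January 1, 2022 against October 25, 2021), points towards T1 at intake. It pairs baseline collection with recruitment. Its Pre-Intervention Assessment section also asks all eligible families whether they would give saliva, a question that fits best before allocation is known. The SAP sentence is a one-line summary: it says families receive the surveys, not when they complete them, and it does not mention notification. All this is fair. It shows that the Protocol is compatible with T1 first. It does not make that a requirement, and it leaves the SAP's stated order in place.

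Second, the SAP's sentence on repeat surveys can be read as planning a comparison of T2 scores alone, for which contamination of T1 costs nothing. That reading is possible, but the SAP does not commit to it.

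Third, re-ordering does not always reduce total bias (Step 3), and for b > 0 with k < r the bias under the current order runs against the intervention. This stands, and it limits what can be claimed. It is no reason to keep the order, since the offset would be accidental and depends on unknown k and r.

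Fourth, b, k and r are all assumed; 0.86 is a reliability for one scale, not a T1–T2 correlation in this trial. The saliva route concerns a subsample of 40 and arises only if families are told of their selection before their T1 survey. With a preliminary efficacy aim, one could call the point minor. These arguments bear on how much weight to give it, not on whether the gap exists.

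**Conclusion.** The concern holds as a conditional risk. The SAP states an order in which T1 surveys follow assignment, families are unblinded, and nothing in either document requires T1 to be completed before the group is known. It is not shown that disclosure does precede T1.

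If families know their group at T1 and the analysis uses T1, the contribution from contamination is −b for change scores and about −r·b for adjusted analyses. For assumed b of 0.1 to 0.2 SD and r of 0.5 to 0.86, that is 0.10 to 0.20 SD and 0.05 to 0.172 SD in absolute size. It is zero if b = 0 or if only T2 is compared. Protecting T1 makes all three analyses estimate the same T2 difference. What then remains, k·b, is the ordinary limitation of an unblinded trial with self-reported outcomes. The change should be made because it is cheap, not because harm has been demonstrated. Confidence is medium.

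**What to change.** Replace the SAP sentence on the order of steps with wording such as: *Each family completes the prescreening tool and the whole T1 survey battery before it is randomized or, at the latest, before its group is revealed to it.* State the same order in the Protocol under Participant Recruitment and Pre-Intervention Assessment. Sources of Materials does not conflict and can stay as it is.

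The second limb also covers the saliva route: because selection reveals the group, a family would be told of it only after its T1 survey is in. The change concerns the surveys, not the saliva samples, which may still follow assignment.

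The cost is a re-ordering of steps already planned. The battery is online and takes 15 to 20 minutes, and the checklist already precedes randomization. If randomizing first is easier, withholding the result until T1 is complete is enough. If the team already works this way, the edit only records it. The downside is a slightly longer wait before families learn their group.
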